### **3.4 SAFETY PLAN**

The safety assessments to be conducted for this study are listed in Section 4.5 and Appendix A.

Serious adverse events of intravitreal injection such as endophthalmitis, retinal detachment and significant vitreous hemorrhage will be reported and monitored. Potential serious adverse events related to study drug such as significant uveitis, hypertension, thromboembolic event, or poor wound healing will be reported and monitored. Serious ocular adverse events such as major subretinal hemorrhage, vitreous hemorrhage and 6-line loss rate will be reported and monitored. Serious adverse events such as hospitalizations, surgeries, emergency room admissions and death will be reported and monitored.

Given the small population studied in this Phase I trial, it will be difficult to estimate the adverse event occurrences. Unmasking procedures or treatment recommendations related to drug or the study in particular are not necessary. Any death in the study population will lead to review and assessment while withholding drug injections for enrolled patients until fully reviewed. If two or more patients suffer thromboembolic events, drug injections will also be withheld for all enrolled patients until review and assessment occur.

### **3.5 COMPLIANCE WITH LAWS AND REGULATIONS**

This study will be conducted in accordance with current U.S. Food and Drug Administration (FDA) Good Clinical Practices (GCPs), and local ethical and legal requirements.

## 4. **MATERIALS AND METHODS**

### 4.1 SUBJECTS

#### 4.1.1 **Subject Selection**

Twenty subjects from one site in the United States will be enrolled. Subjects with active, exudative-PCV who have provided informed consent will be eligible. Subjects who completed the 24 month follow up in the original FVF3671s 0.3 mg or 0.5mg PCV protocol may enter the extension study with 2.0 mg without necessarily demonstrating active exudative PCV at enrollment. (See Appendix A, the study flow chart, for screening assessments.)

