### **2.0 mg Ranibizumab cohort**

Twenty eyes will be treated; PCV eyes may be treatment naïve or received previous PCV therapy greater than 30 days prior to enrollment. A maximum of 10 eyes that completed 24 month enrollment in our study evaluating 0.3 mg or 0.5mg Ranibizumab may be included. *Eyes will be treated with 3 monthly doses of 2.0 mg ranibizumab followed by 2.0mg ranibizumab on a PRN dosing regimen for 9 months.*

*In the year 2 off drug treatment period subjects will be contacted via telephone interview for review of adverse events at month 18 and month 24.*

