### **Secondary Outcome Measures**

- Month 3, 6, 9, 12 best corrected visual acuity at 4 meters – rates for gain of 5,10 and 15 or more letters
- Month 3, 6, 9, 12 best corrected visual acuity at 4 meters- rates for loss of 15 or more letters
- Median and Average best corrected visual acuity at 4 meters- gain/loss (letters) at 3,6,9,12 months.
- Mean change from baseline in central foveal thickness over time up to 12 months as assessed on OCT
- Mean change from baseline in macular volume overtime up to 12 months.
- Proportion of patients with no evidence of fluid from CNV as assessed by OCT at 12 months.
- Mean change from baseline in the total area of CNV fluorescein angiographic leakage overtime up to 12 months.
- Mean change from baseline in total area of ICG CNV lesion size (including polyps and deep choroidal vessels) overtime up to 12 months.
- Fluorescein and ICG angiograms and fundus photographs will also be graded at each time point compared to baseline as unchanged, resolved, improved, worsened, or cannot determine. For the FA and ICG evaluations, “resolved” will be defined as no leakage and no evidence of polyps or PCV choroidal lesion; “improved” will be defined as decreased leakage and/or decreased size, number, or hyperfluorescence of polyps and/or PCV choroidal lesion; and “worsened” will be defined as increased leakage and/or increased size, number or hyperfluorescence of polyps and/or PCV choroidal lesion. For fundus photography evaluations, “resolved” will be defined as no evidence of PED, subretinal fluid, hemorrhage, or hard exudate; improved will be defined as a decrease in PED,

subretinal fluid, hemorrhage, or hard exudate; and “worsened” will be defined increase in PED, subretinal fluid, hemorrhage, fibrosis, or hard exudates.

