#### 4.1.2 **Inclusion Criteria**

Subjects will be eligible if the following criteria are met. *Any deviation/waivers granted regarding inclusion/exclusion criteria will be reviewed by the principal investigator and fully documented.*

- Males and Females >18 years of age. *Females of child bearing potential will undergo urine pregnancy testing* and be required to use appropriate methods of birth control.
- ICG and fluorescein angiographic characteristics consistent with active, leaking PCV with subfoveal lesions &/or subfoveal hemorrhage, lipid exudates, PED or fluid diagnosed within the past 6 months or diagnosed as newly active within the past 6 months. Subjects who completed the 24 month follow up in the original FVF3671s protocol may enter the extension study with 2.0 mg without necessarily demonstrating active exudative PCV at enrollment.
- Best-Corrected ETDRS Visual Acuity at 4 meters between 20/20 – 20/800
- Lesion size- no limitations
- Lesion Characteristics- leaking lesions consistent with PCV. No limitations on hemorrhage, fibrosis or atrophy.
- No therapy (includes non foveal laser, PDT, intravitreal steroids, TTT, radiotherapy, or anti-VEGF therapy) or intraocular surgery within the past 30 days for any condition.

- Clear ocular media to allow for photography/angiography.
- Ability to provide written informed consent and comply with study assessments for the full duration of the study

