### 4.8.3 Efficacy Analyses

1. **Primary Endpoint-** See Section 3.3.1

2. **Secondary Endpoints-** See Section 3.3.2

All subjects will be used in analysis of primary and secondary outcome parameters. Rates for the endpoints at the suggested time points will be presented as a % of the patients enrolled. Analysis of Variance will be used to assess for role of variables in for the endpoints. Variables will include # Ranibizumab injections, other therapies, baseline acuity, age, gender, etc.

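### The month-12 no-fluid proportion ignores baseline fluid, although up to 10 of 20 eyes may enter without active exudation

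*Combined protocol and SAP*

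**What the plan says.** **Who may enter.** Section 3.1 (2.0 mg Ranibizumab cohort) plans 20 treated eyes and sets the roll-over limit: "A maximum of 10 eyes that completed 24 month enrollment in our study". Section 4.1.1 asks for active exudative disease in general, but says that subjects who completed the earlier study "may enter the extension study with 2.0 mg without necessarily demonstrating active exudative PCV at enrollment". Section 4.1.2 repeats that exemption within its angiographic criterion.

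**What is counted.** The list of secondary outcome measures in section 3.3 includes the "Proportion of patients with no evidence of fluid from CNV as assessed by OCT at 12 months". It sets no condition on fluid at Day 0.

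**How it is reported.** Section 4.8.3 uses all subjects for the primary and secondary outcomes and adds: "Rates for the endpoints at the suggested time points will be presented as a % of the patients enrolled". It then plans an analysis of variance: "Variables will include # Ranibizumab injections, other therapies, baseline acuity, age, gender, etc". Neither baseline fluid nor roll-over status is named.

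**What is measured at entry.** OCT is part of the Baseline/Day 0 assessments in section 3.1 and appears at Screen and Baseline in the Appendix A flowchart. Fluid status at entry can therefore be read from data already planned.

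**The concern.** The no-fluid proportion will naturally be read as the share of eyes in which 2.0 mg ranibizumab cleared the fluid. It has that meaning only if every eye had fluid at the start. The protocol expressly allows some eyes in without active exudation, and the endpoint credits such an eye if it is dry at both ends of the year.

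This happens with the plan followed exactly. The other OCT and angiographic outcomes in the same list are framed against baseline, either as mean changes or as gradings. The OCT-fluid proportion is not. If some eyes enter dry, a reader of the pooled figure cannot separate eyes that dried on treatment from eyes that had nothing to dry. Section 3.2 says the roll-overs are included partly to learn about potential efficacy in that group, so the ambiguity touches one of the study's own aims.

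**Working it through.** The documents give no expected no-fluid rate and no formal sample size calculation (section 4.8.1), so there is no planned figure to reproduce. The check is how far the pooled rate can move away from the rate in eyes that had fluid.

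**Inputs from the documents**
- Eyes treated: 20 (section 3.1).
- Maximum roll-over eyes: 10 (section 3.1), so 10/20 = 50% of the sample.
- Denominator: all enrolled (section 4.8.3).

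**Assumptions (not in the documents)**
- k: eyes with no OCT fluid at Day 0. Shown at 0, 5 and 10; 10 is the roll-over cap, not a forecast.
- pw: share of eyes wet at Day 0 that are dry at month 12. Central value 30%, range 20% to 50%.
- pd: share of eyes dry at Day 0 that are dry at month 12. Shown at 80% and 100%.
- One eye per subject, and all 20 observed at month 12.

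**Formula**

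Pooled rate = [pw × (20 − k) + pd × k] / 20

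The excess over the wet-eye rate is therefore k × (pd − pw) / 20. It is zero when k = 0, and positive whenever dry eyes stay dry more often than wet eyes become dry.

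**Worked case, pw = 30% and pd = 100%**
- k = 0: (0.3 × 20) / 20 = 6/20 = 30%
- k = 5: (0.3 × 15 + 5) / 20 = 9.5/20 = 47.5%
- k = 10: (0.3 × 10 + 10) / 20 = 13/20 = 65%

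**Range**

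| pw | pd | k = 0 | k = 5 | k = 10 |
|---|---|---|---|---|
| 20% | 80% | 20% | 35% | 50% |
| 20% | 100% | 20% | 40% | 60% |
| 30% | 80% | 30% | 42.5% | 55% |
| 30% | 100% | 30% | 47.5% | 65% |
| 50% | 80% | 50% | 57.5% | 65% |
| 50% | 100% | 50% | 62.5% | 75% |

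Over this grid the excess is 7.5 to 20 percentage points at k = 5 and 15 to 40 at k = 10.

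**Extreme case.** With k = 10 and pd = 100%, the pooled rate is at least 10/20 = 50% even if no wet eye dries. Its exact (Clopper-Pearson) 95% interval would be 27.2% to 72.8%. The wet-eye result would be 0/10, with an upper limit of 30.8%.

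**Precision of the alternative.** The wet-eye denominator is 20 − k: 20, 15 or 10. A result of 3/10 has an exact 95% interval of 6.7% to 65.2%; 6/20 gives 11.9% to 54.3%.

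**The case against.** **The sizes are assumed, and k may be small.** This stands. The documents contain no OCT dry rate. What they say about the disease argues against k near 10: section 1.3 describes lesions that resist standard-dose monotherapy and a need for repeated injections, with a mean of 7.2 injections in the earlier cohort. Against that, section 1.3 also reports a mean thickness reduction of 67 µm at 24 months in that cohort, and the exemption was written for eyes that may be inactive. Neither side fixes k. Stay-dry rates below 80% are possible under as-needed treatment and would shrink the excess.

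**Little depends on this endpoint.** This also stands. It is one of many descriptive secondaries in an uncontrolled Phase I safety study, with no test or decision rule attached. No error rate changes.

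**The plan already leaves room for the split.** Only in part. The variable list in section 4.8.3 is open-ended, and section 4.2 distinguishes treatment-naive from previously treated eyes. Permission is not pre-specification, though, and a previously treated eye is not necessarily a dry one.

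**Two stronger readings that the documents do not support**

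1. *Non-roll-over eyes are also likely to enter dry.* A reader might infer this because eyes may have "received previous PCV therapy greater than 30 days prior to enrollment", because the angiographic criterion accepts signs such as "lipid exudates, PED or fluid diagnosed within the past 6 months", and because no criterion requires OCT fluid at Day 0. Dry entry is thus not strictly excluded, but the wording points the other way. Section 4.1.1 requires active, exudative disease in these subjects, and section 4.1.2 separately asks for "Lesion Characteristics- leaking lesions consistent with PCV". The six-month window reads as recency of diagnosis or reactivation, not as leave to enter inactive.
2. *The mean changes in thickness and leakage area are flawed too.* Dry eyes have less to lose, so a pooled mean would differ from the wet-eye mean. But those outcomes are already referenced to baseline, and a mean over all enrolled eyes correctly describes the enrolled eyes. Preferring the wet-eye mean is a choice of a different quantity, not the correction of an error.

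**Conclusion.** The point holds for one endpoint. As defined, the month-12 no-fluid proportion credits roll-over eyes that enter and remain dry, so it can overstate fluid resolution. The cap of 10 in 20, the exemption and the absence of a baseline condition are all explicit in the text.

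The size is not known. It runs from nothing, if no eye enters dry, to a pooled 65% against a wet-eye rate of 30%, if all 10 permitted roll-overs are used, enter dry and stay dry. The intermediate case of 5 such eyes gives 47.5%. All of these rest on assumed drying rates.

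The consequence is for interpretation of a descriptive secondary result. Using all 20 subjects is right for the safety primary, which is untouched, and including roll-overs is a reasoned choice in section 3.2. This is a change worth considering, not a serious defect.

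**What to change.** Keep all 20 subjects for safety, and keep the pooled no-fluid percentage as written. In section 4.8.3, pre-specify that the month-12 no-fluid proportion will also be reported (a) among eyes with fluid on baseline OCT and (b) separately for eyes dry on baseline OCT, with the number of eyes in each group. Fix this before results are examined, because a split chosen afterwards in 20 open-label eyes would carry less weight.

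The cost is two extra table rows and a baseline fluid reading from an OCT already scheduled; no new visit or test is needed. The downside is precision. The wet-eye row may rest on about 10 eyes, where 3/10 carries an interval of roughly 7% to 65%, so it should be labelled descriptive and not used to compare groups. If every eye has fluid at entry, the wet-eye row simply equals the pooled figure.

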#### 4.1.2 **Inclusion Criteria**

Subjects will be eligible if the following criteria are met. *Any deviation/waivers granted regarding inclusion/exclusion criteria will be reviewed by the principal investigator and fully documented.*

- Males and Females >18 years of age. *Females of child bearing potential will undergo urine pregnancy testing* and be required to use appropriate methods of birth control.
- ICG and fluorescein angiographic characteristics consistent with active, leaking PCV with subfoveal lesions &/or subfoveal hemorrhage, lipid exudates, PED or fluid diagnosed within the past 6 months or diagnosed as newly active within the past 6 months. Subjects who completed the 24 month follow up in the original FVF3671s protocol may enter the extension study with 2.0 mg without necessarily demonstrating active exudative PCV at enrollment.
- Best-Corrected ETDRS Visual Acuity at 4 meters between 20/20 – 20/800
- Lesion size- no limitations
- Lesion Characteristics- leaking lesions consistent with PCV. No limitations on hemorrhage, fibrosis or atrophy.
- No therapy (includes non foveal laser, PDT, intravitreal steroids, TTT, radiotherapy, or anti-VEGF therapy) or intraocular surgery within the past 30 days for any condition.

- Clear ocular media to allow for photography/angiography.
- Ability to provide written informed consent and comply with study assessments for the full duration of the study

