eyes demonstrated decrease lesion size but branching choroidal vessels were unchanged. A press release from QLT Inc. (QLT Inc. 2009) reported results from the EVEREST prospective, randomized study evaluating ranibizumab monotherapy versus PDT monotherapy versus ranibizumab/PDT combination therapy for 61 eyes with Asian PCV. At 6 months the ranibizumab monotherapy, PDT monotherapy, and ranibizumab/PDT combination groups gained 9.2, 7.5, and 10.9 letters, respectively. Complete polyp regression occurred in 29%, 71% and 78% of eyes in the ranibizumab monotherapy, PDT monotherapy, and ranibizumab/PDT combination groups, respectively (QLT Inc. 2009).

The above data evaluating anti-VEGF therapy for PCV is limited by a relatively small number of treated eyes, short follow-up and absence of comparison groups. However, given the encouraging results of the above limited data along with the known favorable results of anti-VEGF therapy for neovascular AMD, as well as the overlap between exudative AMD and PCV, further evaluation of anti-VEGF therapy for PCV is needed. In addition, evaluation of anti-VEGF therapy for PCV has primarily occurred in an Asian population and little or no data exist for African-American and Caucasian populations. In fact, African-Americans are hardly represented in neovascular AMD anti-VEGF trials. Ethnic differences in PCV may well affect treatment responses due to genetic makeup, variances in the natural history of disease, and living environments.

We previously enrolled 20 non-Asian PCV eyes and evaluated intravitreal ranibizumab (0.3mg and 0.5 mg) for exudative PCV. Subjects included 16 African-Americans (12 female, 4 male) and 3 male Caucasians. The mean age was 63.6 years and the mean follow-up for the present ongoing study is 18 months. Mean baseline BCVA was 20/127 (range, 20/16-20/500) and CPT was 298  $\mu$ m. Mean BCVA increased from baseline by 1.2 and 1.5 ETDRS lines at 12 and 24 months, respectively. Four of 14 eyes and 3 of 12 eyes gained  $\geq 3$  lines BCVA at 12 and 24 months, respectively. Mean CPT decreased from baseline by 53  $\mu$ m and 67  $\mu$ m at 12 and 24 months, respectively. Eyes received a mean of 7.2 injections during a mean follow-up of 19 months. Visually

significant ocular adverse events included cataract progression (n=3), mild vitreous hemorrhage (n=2), and macular hole (n=1). No systemic drug-related adverse events were observed.

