### **3.3 OUTCOME MEASURES**

#### **3.3.1 Primary Outcome Measure**

The primary outcome measure for safety and tolerability is the following:

Incidence and severity of ocular and systemic adverse events. Examples include 30 letter loss, major subretinal hemorrhage, involving 75% or more of clinical macula (arcade to arcade), disease-related vitreous hemorrhage, injection-related endophthalmitis, retinal detachment, vitreous hemorrhage, *study drug/procedure* -

related uveitis, incidence and severity of other adverse events, as identified by physical examination, subject reporting, and changes in vital signs.

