### 4.8.2 Safety Analyses

*All non serious and serious* adverse events, angiographic assessments, physical examinations, vital signs, ocular examinations and visual acuity measurements from all 20 subjects will be utilized to summarize safety data for this pilot study.

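### Entry down to 20/800 can admit eyes that cannot record a 30-letter loss, so the all-enrolled loss rate should be shown beside a rate among eyes able to lose 30 letters

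*Combined protocol and SAP*

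**What the plan says.** Section 4.1.2 sets the acuity criterion as "Best-Corrected ETDRS Visual Acuity at 4 meters between 20/20 – 20/800". The same section puts no limit on lesion size, hemorrhage, fibrosis or atrophy.

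Section 3.3.1 defines the primary outcome as the incidence and severity of ocular and systemic adverse events, and then illustrates it: "Examples include 30 letter loss, major subretinal hemorrhage" and several others. Section 3.4 lists the same degree of loss in lines: "vitreous hemorrhage and 6-line loss rate will be reported and monitored". The secondary outcomes include "rates for loss of 15 or more letters" at months 3, 6, 9 and 12.

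On the denominator, Section 4.8.3 says "All subjects will be used in analysis of primary and secondary outcome parameters" and "Rates for the endpoints at the suggested time points will be presented as a % of the patients enrolled". Section 4.8.2 says that data "from all 20 subjects will be utilized to summarize safety data for this pilot study". Section 4.8.4 bases analyses on available cases without imputation.

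No section sets a minimum baseline score for a loss endpoint, a denominator restricted to eyes able to show the loss, or a scoring rule for vision below the chart. Baseline acuity appears in the analysis only as one of the variables for the analysis of variance in Section 4.8.3.

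**The concern.** A letter score has a floor. An eye that starts with fewer than 30 letters cannot lose 30, even if it loses all its vision. Such an eye can never be an event, but it adds one to the denominator. The dilution runs in one direction only: the reported percentage is at or below the rate among eyes able to show the event.

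At stake is how one safety figure is read. In a 20-eye study of a higher dose, few or no 30-letter losses would be taken as reassuring. How reassuring depends on how many eyes could have shown the event, and the planned table does not report that number.

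The other planned summaries do not supply it. Mean and median letter change share the floor. The available-case rule does not remove these eyes, because an eye with a measured follow-up acuity is still counted as a non-event. The analysis of variance on baseline acuity does not alter the rate, and the floor itself could make poor baseline vision look protective.

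**Working it through.** The plan gives no event rate, power or sample-size figure to reproduce. Section 4.8.1 states that no formal calculation was done.

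**Inputs from the documents**
- Entry range 20/20 to 20/800 (Section 4.1.2).
- 30 letters (Section 3.3.1) and 6 lines (Section 3.4), hence 30/6 = 5 letters per line.
- N = 20 (Section 4.1.1).
- Predecessor cohort of 20 eyes (Section 1.3): "Mean baseline BCVA was 20/127 (range, 20/16-20/500", with a mean gain of 1.5 lines at 24 months.
- Up to 10 eyes that completed that study may enter this one (Section 3.1).

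**Assumptions not in the documents**
- Letter score = 85 − 50 × log10(Snellen denominator/20), floor at 0.
- Baseline scores roughly normal, SD 15 to 25 letters. The predecessor range, 20/16 (89.8 letters) to 20/500 (15.1 letters), spans 74.7 letters. Twenty normal observations span about 3.73 SD on average, so the implied SD is 74.7/3.73 = 20, the middle of the assumed range.

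**Step 1: where the floor bites**

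| Snellen | Letters | Can lose 30? | Can lose 15? |
|---|---|---|---|
| 20/127 | 44.9 | yes | yes |
| 20/250 | 30.2 | just | yes |
| 20/500 | 15.1 | no | just |
| 20/800 | 4.9 | no | no |

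Of the 17 eligible five-letter steps from 85 down to 5, five (25 to 5 letters) cannot show a 30-letter loss and two (10 and 5 letters) cannot show a 15-letter loss.

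**Step 2: how many eyes might be affected (30-letter loss)**

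P(baseline < 30) = Φ((30 − mean)/SD). Scenario A gives all 20 eyes the predecessor's baseline mean of 45 letters. Scenario B gives 10 eyes a mean of 45 and 10 returning eyes a mean of 45 + 1.5 × 5 = 52.5, and averages the two probabilities. The rate reported when the true at-risk rate is 10% is 10% × (1 − P).

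| SD | A: P | A: eyes of 20 | A: reported | B: P | B: eyes of 20 | B: reported |
|---|---|---|---|---|---|---|
| 15 | 15.9% | 3.2 | 8.4% | 11.3% | 2.3 | 8.9% |
| 20 | 22.7% | 4.5 | 7.7% | 17.9% | 3.6 | 8.2% |
| 25 | 27.4% | 5.5 | 7.3% | 22.9% | 4.6 | 7.7% |

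Across both scenarios that is about 2 to 5 eyes, and a reported rate of about 7% to 9%.

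**Step 3: effect on what 20 eyes can show**

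With k affected eyes, the at-risk rate is the all-enrolled rate × 20/(20 − k). With zero events, the one-sided 95% upper limit is 1 − 0.05^(1/n), where n = 20 − k.

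| k | One event, all enrolled | One event, at risk | Zero-event upper limit at n = 20 − k |
|---|---|---|---|
| 0 | 5.0% | 5.0% | 13.9% |
| 2 | 5.0% | 5.6% | 15.3% |
| 5 | 5.0% | 6.7% | 18.1% |

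**Step 4: the 15-letter loss**

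Only eyes below 15 letters (worse than about 20/500) are affected. The predecessor's worst eye scored 15.1, so that cohort had none.

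**The case against.** Four objections deserve weight.

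1. *The primary outcome still sees these eyes.* A reader might infer that the primary safety outcome is blind to the worst eyes. It is not. The 30-letter loss is one example within an open-ended adverse-event outcome. Sections 5.1 and 5.2 require worsening of an existing condition to be recorded as an adverse event, Section 5.1 grades its severity, and Section 5.5.2 makes a disabling event serious. An eye at 20/800 that loses its remaining vision can be captured that way. Only the threshold statistic is affected. This objection stands.

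2. *The all-enrolled rate is not wrong.* A reader might infer that the reported figure is simply biased. As a description of the patients enrolled it is arithmetically correct, and that is what Section 4.8.3 says it is. The study is uncontrolled and descriptive, no decision rule uses this rate, and the event count is the same under either denominator. This stands too. What remains is that the figure understates the rate among eyes able to show the event, and the plan gives the reader no means of seeing by how much.

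3. *The 15-letter loss is not affected to the same degree.* A normal curve around the predecessor mean puts some eyes below 15 letters, but that is only the tail of an assumed distribution; no predecessor eye was there. The 15-letter loss is also a secondary outcome. The point rests on the 30-letter loss.

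4. *The shift is small beside the sampling error.* One to three percentage points is little when the exact 95% interval for 2 of 20 runs from 1.2% to 31.7%. True, but imprecision is visible in an interval and this dilution is not. It also runs one way, and removing it costs almost nothing.

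**Conclusion.** The point holds as a cheap reporting improvement. On standard ETDRS scoring, the entry range admits eyes that cannot register the 30-letter (6-line) loss, and the all-enrolled rate therefore understates the rate among eyes that can. If baseline acuity resembles the predecessor cohort, a true 10% is shown as about 7% to 9%. With five such eyes, the upper limit after zero events is 18.1% and not 13.9%.

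This rests on the 85-letter scale with a floor at zero and on the assumed spread of baseline scores. The documents state neither. If off-chart vision were given letter equivalents, low-vision eyes could register larger losses, but the plan has no such rule. If no eye enters below 30 letters, the effect is nil. Hemorrhage, endophthalmitis, retinal detachment and the other listed events are not touched by it.

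**What to change.** Keep the entry range and the all-enrolled rate. In Section 4.8.3, add the following:

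- Report 30-letter loss also among eyes with a baseline score of at least 30 letters, with an exact confidence interval, and state how many enrolled eyes fall below that score.
- Do the same for 15-letter loss among eyes with at least 15 letters, if any eye enters below that.
- State the letter-scoring convention, including how vision below the chart is recorded.
- List any fall to zero readable letters separately with its baseline score. Do not count it as a 30- or 15-letter loss: from 20/800 it is a change of about 5 letters and would be misclassified.
- Reconcile the enrolled-patient denominator of Section 4.8.3 with the available-case rule of Section 4.8.4. A patient without a follow-up acuity who stays in the denominator is counted as a non-event, which pushes the rate in the same direction.

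The cost is a few sentences and one table column. The added rate will look slightly less favourable and its interval will be wider. Data collection and treatment do not change.
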